5.3.2 Efficacy Variables**5.3.2.1 Primary Variable**

The primary endpoint is the incidence of all-cause death, liver-related death, liver decompensation, liver transplantation, hepatocellular carcinoma, and the composite of any of the above outcomes observed during the post-treatment period.

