6.2 Analysis Windows

For efficacy analyses of HCV RNA and resistance, the time windows specified in [Table 2](#) and [Table 3](#) describe how efficacy data are assigned to protocol-specified time points during the Treatment and PT Periods, respectively. All time points and corresponding time windows are defined based on the blood sample collection date.

For analyses of health-related quality of life (QoL) PROs collected throughout the study, the time windows specified in [Table 4](#) will be used.

For laboratory and vital signs data, the time windows specified in [Table 5](#) and [Table 6](#) describe how data are assigned to protocol specified time points during the Treatment and PT Periods, respectively.

If more than one assessment is included in a time window, the assessment closest to the nominal time will be used. If there are two observations equally distant to the nominal time, the latest one will be used in analyses. The only exception to this is for the SVR windows (e.g., SVR₄, SVR₁₂, and SVR₂₄); for these windows, the last value in the window will be used.

If multiple measurements are made on the same day for a safety laboratory parameter or a vital sign parameter, the average of the values will be used in analyses. For summaries of shifts from baseline and potentially significant values, multiple values on the same day will not be averaged; all values will be considered for these analyses.

Table 2. Analysis Time Windows for HCV RNA and Resistance Endpoints (Treatment Period)

Scheduled Visit	Nominal Day (Study Day)	Time Window (Study Day Range)
Day 1/Baseline ^a	1 ^a	≤ 1 ^a
Week 2	14	2 to 21
Week 4	28	22 to 56
Week 12	84	57 to 126
Week 24 ^b	168	127 to 182
Final Treatment Visit ^c		2 to ≤ 2 days after last dose of study drug

a. Day of first dose of study drug.

b. Week 24 Visit is only applicable to subjects assigned to 24 weeks of treatment.

c. The last value within the window will be used to define the Final Treatment visit value. The upper bound of this Final window is Study Drug End Day ≤ 2.

Note: Data must also have Study Drug End Day ≤ 2 for all windows. The result closest to the scheduled time point will be used.

Table 3. Analysis Time Windows for HCV RNA and Resistance Endpoints (Post-Treatment Period)

Scheduled Visit^a	Nominal Day (Study Drug End Day)	Time Window (Study Drug End Day Range)
Post-Treatment Week 4	28	3 to 56
Post-Treatment Week 12	84	57 to 126
Post-Treatment Week 24	168	127 to 266

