6.3 Missing Data Imputation

No data will be imputed for any efficacy or safety analyses except for the PRO questionnaires, for analyses of the HCV RNA endpoints, and for analysis of the persistence of resistance. If a respondent answers at least 50% of the items in a multi-item scale of the SF-36v2, the missing items will be imputed with the average score of the answered items in the same scale. In cases where the respondent did not answer at least 50% of the items, the score for that domain will be considered missing. Similarly, the missing items of the FACIT-F questionnaire will be imputed with the average score of the answered items in the same scale as long as more than 50% (≥ 7 out of 13) of the items in the scale are answered. The SF-36v2 Mental and Physical Component Summary measures will not be computed if any domain is missing.

HCV RNA values will be selected for an SVR analysis based on visit windows as defined in Section 6.2. When there is no HCV RNA value in a visit window based on defined visit windows, the closest values before and after the window, regardless of the value chosen for the subsequent and preceding window, will be used for the flanking imputation described below.

If a subject has a missing HCV RNA value at a post-Day 1 visit but with undetectable or unquantifiable HCV RNA levels at both the preceding value and succeeding value, the HCV RNA level will be considered undetectable or unquantifiable, respectively, at this visit for this subject. In addition, if a subject has an unquantifiable HCV RNA level at the preceding value and an undetectable HCV RNA level at the succeeding value, or vice versa, the HCV RNA level will be imputed as unquantifiable at this visit for this subject. For SVR analysis, if there is no value in the appropriate window after flanking imputation but there is an HCV RNA value after the window, then it will be imputed into the SVR window. Subsequent to this flanking imputation, if a subject is missing a value for the visit window associated with the analysis, the subject will be imputed as a visit failure (i.e., not undetectable or unquantifiable).

If a subject starts another treatment for HCV, then all HCV RNA values for this subject measured on or after the start date of the new HCV treatment will be excluded from analyses. The subject will be considered a failure for summaries of viral response at all time points after the start of the new HCV treatment.

HCV RNA < LLOQ Analyses for SVR

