If a subject is missing an HCV RNA value for the visit window associated with the analysis of SVR after performing the imputations described above, then this value will be imputed with an HCV RNA value from a local laboratory if present; otherwise, the HCV RNA value for this visit will be missing. Subjects with missing HCV RNA data in the analysis window, after imputations, will be imputed as a failure.

HCV RNA Analyses for Relapse and Virologic Failure

If HCV RNA values from the central laboratory are missing but a local laboratory value is present in the appropriate time period, then the local laboratory value will be used to assess post-treatment relapse and on-treatment virologic failure.

Finally, missing sequence data will be imputed as follows in the analysis of the persistence of resistance from the sequences from PT Week 52 through PT Week 260 (5 years). If a signature variant is not detectable by population, clonal or deep sequencing at PT Week 24 (or later), the variant is imputed as not detectable at the PT Week 52 (or timepoints after the sequence with the variant not detectable) and time points thereafter if a sample from Post-Treatment Week 52 or later is not sequenced. If a signature variant is detectable by population, clonal, or deep sequencing at Post-Treatment Week 52 or later, then the variant is imputed as being detectable at earlier time points if the sample at the earlier time point is not sequenced.

7.0 Demographics, Baseline Characteristics, Medical History, and Previous/Concomitant Medications

Demographics, baseline characteristics, medical history, and previous/concomitant medications will be summarized overall and by presence of cirrhosis and genotype 1 subtype on the safety population.

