10.0 Efficacy Analysis

10.1 General Considerations

The primary efficacy analysis on clinical outcomes will be performed on all subjects in the ITT population as defined in Section 5.1. All other efficacy analyses will be performed on the ITT-II population.

Treatment effects will be evaluated based on a two-sided significance level of 0.05 (when rounded to three decimal places). The data from the ITT-II population will be presented in one column/row as it represents the labelled treatment.

Plasma HCV RNA levels will be determined for each sample collected by the central laboratory using the COBAS[®] AmpliPrep/COBAS[®] TaqMan[®] HCV Test, v2.0. The lower limit of quantification (LLOQ) and the lower limit of detection (LLOD) is 15 IU/mL. HCV RNA results that are detectable but not quantifiable are reported as "< 15 IU/mL" and results that are not detectable are reported as "-NON-DETECTED."

Assessment of Clinical Outcomes

Incidence of the following clinical outcome events will be collected during the 12/24 weeks of treatment and the 5-year (PT Week 260) Post-Treatment Period. The data reported on the "Clinical Outcome" eCRFs will be adjudicated by an independent outcome committee and results of the adjudication will be added to the "Clinical Outcome" eCRFs:

- All-cause death: Death due to any cause.
- Liver-related death: Death as the result of a liver-related cause.
- Liver decompensation: Development of any of the following conditions: ascites, hepatic encephalopathy, or variceal bleeding.

- Liver transplantation: any subject who had a liver transplantation
- Hepatocellular carcinoma (HCC): development of HCC in any subject at any time during the study. HCC is defined by histologic confirmation or a > 1 cm mass lesion on cross-sectional imaging that meets the diagnostic criteria for HCC according to EASL guidelines.
- Composite of any of the above outcomes.

Definitions for HCV RNA Efficacy Endpoints

Note that a confirmed quantifiable post-treatment value is defined as two consecutive post-treatment HCV RNA measurements \geq LLOQ. During treatment, a confirmed quantifiable value is defined as any two consecutive HCV RNA values \geq LLOQ, either both during treatment or at the final treatment measurement and the next consecutive post-treatment measurement.

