10.3 Primary Efficacy Analysis

The primary efficacy analysis will be conducted among subjects in the ITT population as described in Section 5.1. HCV RNA values and SVR₁₂ will be imputed as described in Section 6.3.

The primary efficacy endpoint is to assess the effect of response to treatment (as assessed by SVR₁₂ status) on clinical outcomes by comparing the time to incidence of the following events between subjects who achieve SVR₁₂ and those who do not.

- All-cause death
- Liver-related death
- Liver decompensation
- Liver transplantation
- Hepatocellular carcinoma

- Composite of any of the above outcomes

For each of the six event types as listed above, a subject's time to event will be defined as the number of days from the first day of study drug dosing for the subject to the day the subject experiences an event of interest. All events of interest will be included, regardless of whether the event occurred while the subject is still taking study drug or has previously discontinued study drug. If the subject does not experience an event of interest nor has the subject died (all-cause death), the subject's data will be censored at the date of the subject's last available assessment of clinical outcomes. For subjects with no post-baseline assessment, the subject's data will be censored on the first day of study drug dosing. All-cause death is a censoring event for liver-related death, liver decompensation, liver transplantation and hepatocellular carcinoma. Time to the composite of clinical outcomes is the time to the first occurrence of any clinical outcome.

For each of the six event types, the distribution of time to event will be estimated for subjects who have achieved SVR₁₂ and those who haven't using Kaplan-Meier methodology and compared between the subjects who have achieved SVR₁₂ and those who haven't using the log-rank test.

For each of the six event types, the 1-, 2-, 3-, 4-, and 5-year event-free survival rate will be estimated using Kaplan-Meier methodology and a 95% confidence interval will be constructed separately for those who have achieved SVR₁₂ and those who have not. For each of the six event types, a Cox proportional hazards (PH) model will be constructed to include all the baseline characteristics as described in Section 7.1, SVR₁₂ status, and other variables as appropriate.

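### The primary clock starts at first dose, but the groups are set by SVR12 months later, so every death before the SVR12 window counts against the non-SVR12 group

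*SAP*

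**What the plan says.** SAP 10.3 defines the time origin for all six event types: "a subject's time to event will be defined as the number of days from the first day of study drug dosing". It adds: "All events of interest will be included, regardless of whether the event occurred while the subject is still taking study drug". It then compares subjects with and without SVR12 by Kaplan-Meier, log-rank and Cox, with SVR12 entered alongside the baseline characteristics and not described as time-dependent.

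SVR12 is read in Study Drug End Days 57 to 126 (SAP 6.2, Table 3). Where a window holds several values, "for these windows, the last value in the window will be used".

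SAP 10.3 applies the Section 6.3 imputation to the primary analysis. If flanking leaves the window empty but "there is an HCV RNA value after the window, then it will be imputed into the SVR window". A local-laboratory value may then be used. Failing that: "Subjects with missing HCV RNA data in the analysis window, after imputations, will be imputed as a failure".

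For the cause-specific endpoints, "All-cause death is a censoring event for liver-related death, liver decompensation, liver transplantation and hepatocellular carcinoma".

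No landmark, delayed entry or time-dependent SVR12 is given. The sensitivity analyses in SAP 10.6 concern only the SVR12 percentage.

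The event period also differs between documents. Protocol 5.3.2.1 refers to the "composite of any of the above outcomes observed during the post-treatment period", whereas under SAP 10.1 events "will be collected during the 12/24 weeks of treatment and the 5-year (PT Week 260) Post-Treatment Period".

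**The concern.** Group membership depends on something that happens after the clock has started. To be counted as SVR12, a subject must normally live long enough to give a sample in or after the window. A subject who dies earlier cannot do so, whatever the viral response, and is placed in non-SVR12. The SVR12 group therefore contains no deaths before the window, and all of them fall on the small non-SVR12 group. The back-fill from later values also requires survival.

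Baseline covariates in the Cox model cannot correct this, because the assignment uses later survival.

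The problem is not automatic for decompensation, transplantation or HCC. A subject with one of these before the window can survive and still achieve SVR12.

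At stake is the study's primary question, whether SVR12 lowers later event rates. The rule moves the hazard ratio toward SVR12 even if SVR12 has no effect.

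**Working it through.** **1. When SVR12 is known, counted from first dose**

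| Treatment completed | Window opens | Nominal | Window closes |
|---|---|---|---|
| 12 weeks (84 days) | 84+57 = Day 141 | 84+84 = Day 168 | 84+126 = Day 210 |
| 24 weeks (168 days) | 168+57 = Day 225 | 168+84 = Day 252 | 168+126 = Day 294 |

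Subjects who stop early reach the window sooner, because SVR12 counts from the last actual dose.

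**2. The plan's own power figure**

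Inputs (SAP 4.3): N = 2,000, 4% non-SVR12, 20% five-year composite rate in non-SVR12, HR 0.25, dropout up to 20%. With exponential event times and dropout, expected events are 14.4 + 93.5 = 107.9. Schoenfeld power is Φ(√(107.9 × 0.04 × 0.96) × ln 4 − 1.96) = Φ(0.86), about 80.5%, so the stated figure of more than 80% reproduces. Simulated log-rank power is higher, about 98%. Schoenfeld's formula assumes that 4% of events fall in the non-SVR12 group, whereas here it is 14.4/107.9 = 13%.

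**3. How many early deaths to consider**

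The documents do not say, so a range is needed.

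- Low anchor: protocol Table 2 shows one death among 770+401+509+208+172 = 2,060 actively treated subjects. The exact 95% interval is 0.02 to 5.4 per 2,000, for the treatment-emergent period only.
- High anchor: a constant hazard at an assumed 5% five-year mortality gives 2,000 × (1 − 0.95^(141/1826.25)) = 7.9 deaths by Day 141.

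**4. Hand check with no true effect**

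Take five-year mortality of 6.7% (the SVR figure in protocol 3.0), so the yearly hazard is h = −ln(0.933)/5 = 0.01387. With d early deaths moved into a group of 80, each assumed to contribute about 0.2 years:

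rate ratio = h ÷ [(80 × 0.067 + d) / (80 × 0.067/h + 0.2d)]

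- d = 1: 0.01387 ÷ (6.36/386.6) = 0.84
- d = 2: 0.73
- d = 4: 0.01387 ÷ (9.36/387.2) = 0.57
- d = 8: 0.40

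The true ratio is 1 in every case.

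**5. Simulation with no true effect**

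N = 2,000, 4% non-SVR12, 20% dropout, later five-year mortality 5% (assumed) or 6.7%, five-year non-fatal rate 5% (assumed), 2,000 runs per scenario. Rejection at a nominal two-sided 5%:

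| Early deaths | All-cause death | Composite | Median death HR |
|---|---|---|---|
| 1 | 9–10% | 8% | 0.82–0.87 |
| 2 | 18–20% | 13% | – |
| 4 | 40–48% | 29–32% | 0.48–0.56 |
| 8 | 83–89% | 68–72% | – |

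The non-fatal outcomes combined stay at 4–5%. A landmark at Day 210 gives 3.6–5.0% for death and 5.1–5.5% for the composite. Repeat runs with separately written code gave 9–12% for death at one early death and 42–55% at four.

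**6. Simulation under the planned HR of 0.25**

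Assumed split in non-SVR12: five-year death 10%, non-fatal 11%.

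| Early deaths | Composite HR | Death HR |
|---|---|---|
| 1 | 0.23 | 0.23 |
| 4 | 0.20 | 0.16 |
| 8 | 0.16 | 0.12 |

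The landmark gives 0.25–0.26.

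**7. Would the protocol's post-treatment rule suffice?**

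No. For a subject treated the full 12 weeks, End Days 1–56 come before the window, and 56/141 is about 40% of the exposed time.

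**The case against.** The strongest objection is that early deaths may be very few. Eligibility excludes Child-Pugh scores of 7 or more, prior decompensation and confirmed HCC, and Phase 3 points to about one death per 2,000. Eight exceeds the upper Phase 3 limit of 5.4 and rests on a constant hazard. That stands: the rows for one to four deaths are the most relevant, and at one death the distortion is modest. However, Phase 3 covers only the treatment-emergent period, while exposure here lasts until the SVR12 window.

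Liver-related death has not been sized separately. The one Phase 3 death was from lung cancer, so it would count toward all-cause death and the composite only. That also stands; for liver-related death the claim concerns mechanism and direction.

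Protocol 5.6.1 calls the analyses descriptive. A biased hazard ratio misleads as a description too, and SAP 4.3, 4.4 and 10.3 set power, alpha and log-rank tests.

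A landmark has its own cost. Fixing status at Day 126 drops the Section 6.3 back-fill, so some living responders with a missed sample would count as non-SVR12. If 20 did (an assumed number), the group's relative hazard would be (80 + 20 × 0.25)/100 = 0.85, and a true HR of 0.25 would read 0.25/0.85 = 0.29. This dilutes the effect rather than exaggerating it, but it is a reason to specify the sensitivity analyses below.

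**Conclusion.** The concern holds and the analysis should be changed. The timing, the imputation route and the direction of bias follow from the SAP's own rules. Only the size depends on assumptions: the number of early deaths, exponential event times, the split between fatal and non-fatal events, and dropout.

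At about one early death the null hazard ratio for death is pulled to roughly 0.85. At four it is about 0.5, with false rejection near one half. If the true effect is as large as planned, the harm is an exaggerated hazard ratio rather than a wrong significance call. The bias is not automatic for decompensation, transplantation or HCC.

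**What to change.** In SAP 10.3:

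- Start the primary clock at a fixed landmark, Study Drug End Day 126, with subjects alive, under follow-up and free of the event in question on that day.
- Take SVR12 status from data up to the landmark. State in advance that living subjects with no status by then count as non-SVR12, and say that this departs from Section 6.3, which would first look to later values.
- Add sensitivity analyses that (a) exclude those subjects and (b) apply the Section 6.3 back-fill.
- Tabulate events before the landmark by type, and keep the first-dose clock as a sensitivity analysis.
- Reconcile protocol 5.3.2.1 with SAP 10.1 and 10.3 on the event period.

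SVR12 as a time-dependent covariate is an acceptable alternative.

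The cost is wording and programming, with no new data. The ITT wording for the primary analysis needs adjusting, and the TOPAZ-I plan should match because the data are pooled. Power should be restated, because events before the landmark leave the comparison. Simulated composite power falls from 98.0% to 96.7%. Schoenfeld power changes as follows:

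| N | First dose | Landmark Day 210 | Landmark Day 294 |
|---|---|---|---|
| 2,000 | 80.5% | 74.9% | 72.3% |
| 2,250 | 84.9% | 79.7% | 77.2% |

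The Schoenfeld figures end follow-up five years after first dose, so they are slightly pessimistic.

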Moderate ascites = Ascites manifested by moderate symmetrical distension of the abdomen.

Severe ascites = Large or gross ascites with marked abdominal distension.

** Grade 0: normal consciousness, personality, neurological examination, electroencephalogram.

Grade 1: restless, sleep disturbed, irritable/agitated, tremor, impaired handwriting, 5 cps waves.

Grade 2: lethargic, time-disoriented, inappropriate behavior, asterixis, ataxia, slow triphasic waves.

Grade 3: somnolent, stuporous, place-disoriented, hyperactive reflexes, rigidity, slower waves.

Grade 4: unarousable coma, no personality/behavior, decerebrate, slow 2 to 3 cps delta activity.

Clinical Assessment of Liver Decompensation

A clinical assessment of hepatic encephalopathy and ascites will be performed at Study Day 1 prior to dosing to confirm the subject has not progressed to hepatic decompensation since screening for all subjects who have compensated cirrhosis. Grading system guidelines for ascites are listed above in [Table 9](#).

Hepatocellular Carcinoma Screening: Liver Ultrasound

In order to monitor for the presence of hepatocellular carcinoma (HCC), an ultrasound of the liver will be performed as indicated in [Table 7](#).

For subjects with compensated cirrhosis:

- Subjects receiving 12 weeks of treatment will have a liver ultrasound performed at the screening visit and all Post-Treatment visits except Post-Treatment Week 4
- Subjects receiving 24 weeks of treatment will have a liver ultrasound performed at the screening visit, Week 24 visit, and all Post-Treatment visits except the Post-Treatment Week 4 and Post-Treatment Week 12.

For subjects without cirrhosis: Liver ultrasound will be performed at the Screening Visit, Post-Treatment Week 52, Post-Treatment Week 156 and Post-Treatment Week 260.

Subjects with a historical negative liver ultrasound, CT or MRI (within 3 months prior to screening) are not required to undergo a screening ultrasound.

A positive Ultrasound result suspicious for HCC during the treatment or post-treatment period will be confirmed with CT scan or MRI.

Assessment of Clinical Outcomes

The following clinical outcomes will be assessed during the study at visits outlined in **Table 7:**

- All-cause death: Death due to any cause.
- Liver-related death: Death as the result of a liver-related cause, based on the opinion of the clinical site principal investigator.
- Liver transplantation: Any subject who had undergone liver transplantation.

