5.3.4 Pharmacogenetic Variable

IL28B status will be determined for each subject and analyzed as a factor contributing to the subject's response to study treatment. These IL28B genotype results may be analyzed as part of a multi-study assessment of IL28B and response to ABT-450, ABT-267, ABT-333, or drugs of these classes. The results may also be used for the development of diagnostic tests related to IL28B and study treatment, or drugs of these classes.

5.4 Removal of Subjects from Therapy or Assessment**5.4.1 Discontinuation of Individual Subjects**

Each subject has the right to withdraw from the study at any time. In addition, the investigator may discontinue a subject from the study at any time if the investigator considers it necessary for any reason, including the occurrence of an adverse event or noncompliance with the protocol.

Subjects that discontinue study regardless of cause should be contacted (minimally as a telephone assessment) at each scheduled yearly visit to collect the survival status only if they provide consent. Details regarding informed consent are provided in Section 9.3.

If the subject prematurely discontinues during the Treatment Period or the Post-Treatment Period, the procedures outlined for the applicable Premature D/C Visit should be completed as defined in [Table 7](#). Ideally for study drug discontinuation, this should occur on the day of study drug discontinuation, but no later than 2 days after their final dose of study drug and prior to the initiation of any other anti-HCV therapy. However, these procedures should not interfere with the initiation of any new treatments or therapeutic modalities that the investigator feels are necessary to treat the subject's condition.

Following discontinuation of study drug, the subject will be treated in accordance with the investigator's best clinical judgment. The last dose of any study drug and reason for discontinuation from the Treatment Period will be recorded in the EDC (electronic data capture) system.

If a subject has an ongoing adverse event or an unresolved laboratory result that is significantly outside of the reference range at the time of study drug discontinuation, the investigator will attempt to provide follow-up until a satisfactory clinical resolution of the laboratory result or adverse event is achieved.

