9.3 Subject Information and Consent

The investigator or his/her representative will explain the nature of the study to the subject, and answer all questions regarding this study. Prior to any study-related screening procedures being performed on the subject, the informed consent statement will be reviewed and signed and dated by the subject, the person who administered the informed consent, and any other signatories according to local requirements. A copy of the informed consent form will be given to the subject and the original will be placed in the subject's medical record. An entry must also be made in the subject's dated source

documents to confirm that informed consent was obtained prior to any study-related procedures and that the subject received a signed copy.

If a subject continues on DAA after becoming pregnant during the treatment, the subject should sign the informed consent approved by their IRB. A copy of the informed consent form will be given to the subject and the original will be placed in the subject's medical record.

Informed consent should also be obtained if a subject discontinues early from the study and agrees to be contacted over the telephone at each scheduled yearly visit to collect the survival status. A copy of the informed consent form will be given to the subject and the original will be placed in the subject's medical record.

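### SAP 10.3 gives all six primary events one undefined censoring date, although study discontinuers are followed for survival only; no single reading of that date suits both death and the liver events

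*SAP*

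**What the plan says.** SAP 10.3 defines time to event "For each of the six event types as listed above" (all-cause death, liver-related death, decompensation, transplantation, HCC and their composite). A subject who has neither the event nor died is "censored at the date of the subject's last available assessment of clinical outcomes". The only event-specific addition is that death from any cause censors the other four single events. On what counts, the SAP says: "All events of interest will be included, regardless of whether the event occurred while the subject is still taking study drug". That sentence deals with stopping study drug. It does not mention leaving the study.

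Protocol 5.4.1 says that subjects who leave the study "should be contacted (minimally as a telephone assessment) at each scheduled yearly visit to collect the survival status only if they provide consent". Protocol 9.3 describes the consent for this: the subject "agrees to be contacted over the telephone at each scheduled yearly visit to collect the survival status". Neither section mentions collecting a liver outcome at that contact.

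Protocol 5.3.1.1 treats the assessment of clinical outcomes as a visit procedure: "The following clinical outcomes will be assessed during the study at visits outlined in" Table 7. The SAP never mentions the survival contact and does not define the last available assessment.

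**The concern.** The rule needs one date per subject, but for a consenting study discontinuer two different things are known. Vital status is known up to the last yearly contact. Liver status is known only up to the last study visit.

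- **Assessment means a Table 7 visit.** A discontinuer who dies later is an event on the death date. One who is contacted in the same way and found alive is censored back at the last visit. Time after discontinuation enters the risk set only for those who go on to die.
- **The survival call counts as an assessment for every event.** The death analysis is then sound. For decompensation, transplantation and HCC, however, the subject accrues event-free time in years when nobody looked.

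The composite has both problems. At stake are the 1- to 5-year Kaplan-Meier estimates that SAP 10.3 promises for each SVR12 group and, under a further condition, the comparison between the groups.

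**Working it through.** **Inputs from the documents.** Two-sided alpha 0.05 (SAP 4.4). At least 2000 subjects, 4% without SVR12, 20% five-year composite rate without SVR12, hazard ratio 0.25, dropout up to 20%, power above 80% (SAP 4.3). Five-year all-cause mortality 6.7% with SVR and 14.4% without, from a pegylated interferon/ribavirin cohort (Protocol 3.0).

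**Assumed.** Constant hazards, discontinuation independent of death, a five-year horizon, consent fraction c between 0 and 1, and discontinuation other than 20% as illustration only.

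**Step 1: the plan's own figure.** The SVR12 five-year rate is 1 − 0.8^0.25 = 5.43%. With exponential dropout reaching 20% at five years, 107.9 events are expected. Schoenfeld power is Φ(|ln 0.25| × √(0.04 × 0.96 × 107.9) − 1.96) = Φ(0.86) = 80.6%. The stated power is reproduced, so 20% is used below as the five-year discontinuation probability.

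**Step 2: mortality when assessment means a Table 7 visit.** Let λ be the death hazard, δ the discontinuation hazard, S(t) = exp(−λt) and G(t) = exp(−δt).

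- Observed death density: λS(t)[G(t) + c(1 − G(t))].
- At risk at t: S(t)G(t) + c(1 − G(t))[S(t) − S(5)]. The second term holds only discontinuers who will die before year 5.
- Kaplan-Meier limit: 1 − exp(−∫ density / at-risk dt) over 0 to 5 years.

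Hazards per year: λ = −ln(0.856)/5 = 0.0311 without SVR12 and −ln(0.933)/5 = 0.0139 with SVR12; δ = −ln(0.8)/5 = 0.0446 for 20% discontinuation.

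| Discontinuation (both groups) | Consent | True 14.4% reads | True 6.7% reads |
|---|---|---|---|
| 10% | 100% | 15.1% | 7.0% |
| 20% | 100% | 15.9% | 7.5% |
| 20% | 50% | 15.2% | 7.1% |
| 20% | 0% | 14.4% | 6.7% |

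At 20% discontinuation and 50 to 100% consent, the relative overstatement is about 5 to 11%. Simulation of the 20% settings with 50% and 100% consent agreed within 0.1 percentage point. Censoring at the last date known alive returns the true values in every row.

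**Step 3: hazard ratio on the same reading.** Large-sample Cox score equation, group shares 4:96, true ratio ln(0.933)/ln(0.856) = 0.446.

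| Discontinuation, non-SVR12 / SVR12 | Consent 100% | Consent 50% |
|---|---|---|
| 20% / 20% | 0.447 | 0.447 |
| 40% / 20% | 0.393 | 0.416 |
| 60% / 20% | 0.332 | 0.377 |

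**Step 4: liver events when the call counts as an assessment.** With full consent and deaths ignored, events are seen only before discontinuation while everyone stays at risk. The estimate is λ/(λ + δ) × (1 − exp(−5(λ + δ))). For an illustrative true risk of 20% (λ = 0.0446) and 20% discontinuation, this is 0.5 × (1 − 0.64) = 18.0%. At 40% discontinuation (δ = 0.1022) it is 0.304 × (1 − 0.48) = 15.8%.

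**The case against.** The strongest reply is that the text does not fix the literal reading. All-cause death is itself a listed clinical outcome, and Protocol 5.4.1 calls the yearly contact a telephone assessment. Because the rule is applied to each event type, one could take the last assessment separately by event: the survival contact for death and the Table 7 visit for liver events. Mortality would then be unbiased and mainly the composite would be left open. This stands as a sensible intention, but the SAP does not state it, and a programmer could follow any of the three readings.

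Size is also a fair point. At the planned 1650 + 600 = 2250 subjects, 4% is 90 without SVR12, with about 13 deaths at 14.4%. The standard error of that proportion is √(0.144 × 0.856/90), about 3.7 points, against a shift of 0.8 to 1.5. The log hazard ratio has a standard error of about √(1/13 + 1/145) = 0.29, against a shift of ln(0.446/0.393) = 0.13 even in the 40%/20% full-consent case. The effect is modest beside sampling error, but it is systematic and avoidable.

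A reader might also infer that non-SVR12 subjects leave in order to be retreated. The plan points the other way: anti-HCV medication is recorded throughout the post-treatment period (Protocol 5.2.3), and subjects starting new HCV treatment stay in the analysis as virologic failures (SAP 6.3). Finally, the survival-contact clause is visible only in this protocol. Whether TOPAZ-I, which supplies 1650 of the 2250 subjects, has the same clause is not shown.

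**Conclusion.** The point holds as a defect of specification with a calculable consequence. One undefined date cannot serve both death and the liver events: a Table 7 reading overstates mortality whenever some discontinuers consent, and a call-counts-for-all reading understates liver events. At 20% discontinuation the first costs about 0.8 to 1.5 points on 14.4% and 0.4 to 0.8 on 6.7% for 50 to 100% consent; the second turns a true 20% into about 18.0%.

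Two stronger inferences are not supported. The first is that mortality is overstated outright: this depends on an undefined term and on consent, and vanishes at zero consent. The second is that the SVR12 comparison is biased: with equal discontinuation the hazard ratio is 0.447 against 0.446. It moves in favour of SVR12 only if non-SVR12 subjects discontinue more. That is plausible, because SAP 6.3 says "Subjects with missing HCV RNA data in the analysis window, after imputations, will be imputed as a failure", which tends to place early leavers in the non-SVR12 group. The documents give no discontinuation rate by SVR12 status, so the 40%/20% result (about 0.45 to 0.39) is illustration only.

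All sizes rest on constant, independent hazards and, for mortality, on rates from an interferon-era cohort.

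**What to change.** State the censoring date by event in SAP 10.3:

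- **All-cause death:** date last known alive, including the yearly survival contacts.
- **Decompensation, transplantation, HCC:** last Table 7 clinical-outcome assessment. For study discontinuers, a death learned later through the survival contact should not move this date forward.
- **Liver-related death:** date last known alive only if cause of death is obtained and adjudicated for deaths after discontinuation; otherwise stop at study discontinuation. A survival-status call alone may not supply the cause.
- **Composite:** while a subject is on study, count all events, including deaths between visits. For study discontinuers, censor at the last clinical-outcome assessment before they left and exclude deaths learned only through the survival contact. Add a sensitivity analysis that includes those deaths.

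The composite rule should not be shortened to counting events only up to the last full visit for everyone. Visits are yearly after Post-Treatment Week 52, so that would also drop between-visit deaths of subjects still on study.

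The cost is SAP wording, a survival-contact date in the analysis dataset, and a few post-discontinuation deaths lost from the main composite analysis. The same rule should be confirmed for the TOPAZ-I data before pooling.
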